consisting of one 12-minute run. During the trauma cue, participants will hear an audio recording describing their traumatic event. During the blocks of neutral cue, participants will hear an audio recording describing their relaxing scenario. During the substance cue, participants will hear an audio recording describing in detail the last time they consumed alcohol or drugs. To minimize potential carry-over effects, the runs will be counterbalanced so that half of the participants in the placebo group and half of the participants in the treatment group are exposed to the trauma cue first and the remaining participants in each group are exposed to the substance cue first. T2*-weighted gradient-echo planar images (EPI) will be acquired with the following parameters: TR = 2000 ms, TE = 27 ms, flip angle = 76°, matrix 64 x 64, field of view = 23 cm, slice thickness = 3.7 mm with no gap, with 36 slices to cover the entire brain.

[figure not shown]

Fig 5. Overview of fMRI neuroimaging session. Assessment of (a) resting state connectivity, and (b) response to trauma, alcohol and neutral cues.

Statistical Analyses

General. Baseline clinical and demographic characteristics will be collected and contrasts performed between treatment groups. Continuous and ordinal characteristics will be compared using a Wilcoxon Rank-Sum test statistic while categorical characteristics will be compared using a Pearson Chi-Square test statistic. All analyses will be performed on the intent-to-treat sample consisting of all randomized subjects.

Randomization. The randomization will be stratified by (1) PTSD severity (PCL total score) and (2) AUD severity (AUDIT total score) for a total of four strata. Urn randomization will be employed to balance the randomization assignment with respect to these strata. The purpose of stratification is to distribute these potential prognostic factors equally across treatment groups. To the extent that the stratification variable is predictive, stratifying on it may enhance statistical power to identify treatment effects.

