individuals who relapsed (n=24) during treatment had significantly lower PFC-AMY connectivity at baseline as compared to individuals who did not relapse (n=21) (McHugh et al., 2014). The effect size for this reduction was 1.0. Thus, power (1- β) reaches .80 with only 34 total participants (two-tailed, alpha=.05). The present study is therefore well-powered to test the proposed hypotheses.

Missing Data. We will perform attrition analyses on whether participants and dropouts differ on key variables, and whether variables on which they differ interact with treatment to affect outcome measures. As participants will be randomized to treatment, it is unlikely that missing data will produce biased estimates of treatment effect, as observed and unobserved covariates should theoretically be balanced across treatment groups. In addition, in general, less than 10% missing data have little impact on power and do not introduce bias, regardless of the missing data mechanism. Larger proportions of data missing at random (MAR) or missing not at random (MNAR) could potentially bias study findings and reduce power. If the percent missing data are greater than 10%, propensity score methods will be used for data imputation. In the propensity score method, first the distribution of the missing indicator variable given the observed data is modeled to derive a propensity score. Then observations are grouped on these propensity scores and an approximate Bayesian bootstrap imputation is applied to each group.

Hypotheses. The hypotheses and statistical approaches for testing each hypothesis are listed below. An experienced biostatistician at MUSC ([name], Department of Public Health) who has worked with our group for the past five years will collaborate with [name] (Director of the CAP Data Management and Biostatistics Core) as needed during the project to ensure consistency across sites with regard to scoring and analysis of dependent measures.

Hypothesis 1: Participants who receive doxazosin, as compared to placebo, will evidence significantly greater reductions in PTSD severity. To test this hypothesis, generalized linear mixed effects models will be employed to assess reduction in CAPS-5 and PCL-5 total scores during the treatment phase. Restricted maximum likelihood (REML) methods will be used to estimate the fixed effects and variance components, and model based treatment effect estimates will be used to construct group level tests over time.

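### At the planned dropout the imputation step is expected to apply, yet it does not keep donors within arm; if its values feed the tests, it can dilute the treatment effect

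*Combined protocol and SAP*

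**What the plan says.** The combined protocol and SAP treats the topic under Statistical Analyses, Missing Data.

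- **Rationale.** "As participants will be randomized to treatment, it is unlikely that missing data will produce biased estimates of treatment effect", because covariates should be balanced between the arms. The next sentence, introduced by the qualifier *in general*, holds that "less than 10% missing data have little impact on power and do not introduce bias, regardless of the missing data mechanism". The section then concedes: "Larger proportions of data missing at random (MAR) or missing not at random (MNAR) could potentially bias study findings and reduce power".
- **Trigger.** "If the percent missing data are greater than 10%, propensity score methods will be used for data imputation". Whether the percentage counts participants, visits or variables is not stated.
- **Method.** The first step models who is missing, using whatever was observed, and turns the fitted chance into a score. The second step fills in the values, and its wording makes no mention of arm: "observations are grouped on these propensity scores and an approximate Bayesian bootstrap imputation is applied to each group".
- **Attrition analyses.** Dropouts are compared with other participants, and the plan examines "whether variables on which they differ interact with treatment to affect outcome measures". No step links the result to the primary estimate.

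The General paragraph adds: "All analyses will be performed on the intent-to-treat sample consisting of all randomized subjects". Hypothesis 1 names a mixed model fitted by REML to CAPS-5 and PCL-5. Hypothesis 2 names a logistic regression of abstinence in weeks 9 to 12 and GEE models of weekly abstinence. Neither mentions imputed values. The Power paragraph expects about 30% dropout and randomizes 144. The Data Safety and Monitoring section only refers missing data back to the statistical plan.

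**The concern.** With dropout near 30%, the imputation paragraph is likely to be used, and it leaves the choices that matter to whoever runs it. A group formed only on the chance of being missing contains participants from both arms. If a missing doxazosin outcome can be filled with a placebo participant's value and the reverse, the filled-in part of the sample carries little or no treatment difference. The estimate moves toward zero and power is lost. If only one imputation were drawn and analysed as real data, the standard error would be too small and type I error too high. Two analysts could both comply with the paragraph and report different results, and the choice could be made after the data are seen.

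The supporting rationale is also unsound. Randomization balances the arms at entry; dropout comes later and can depend on arm and response. No missing fraction above zero removes bias under every mechanism.

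**Working it through.** **1. Which branch applies.** The Power paragraph gives 100 evaluable and about 30% dropout. 100/0.7 = 142.9; by arm, 50/0.7 = 71.4, rounded up to 72, so 144 in total. The plan's figure reproduces. The implied loss is (144 - 100)/144 = 30.6%, three times the 10% trigger when counted in participants.

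Planned CAPS effect: 31% against 20% reduction, SD 20, difference 11 points. At 50 per arm, 11/(20 x sqrt(2/50)) = 2.75, and Phi(2.75 - 1.96) = 0.785 (two-sided 5% assumed), close to the stated 80%.

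**2. Expected dilution.** Let a fraction d drop out in each arm, with donors drawn regardless of arm. Imputed values then have the same expectation in both arms, so

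expected difference = (1 - d) x true difference + d x 0.

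- CAPS: 0.7 x 11 = 7.7 points.
- Abstinence, 32% against 10%: 0.7 x 22 = 15.4 percentage points.

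Even with 72 filled-in values per arm treated as real, SE = 20 x sqrt(2/72) = 3.33, and power = Phi(7.7/3.33 - 1.96) = Phi(0.35) = 0.64.

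**3. Simulation, CAPS.** All of the following is assumed, since the documents give no dropout model: 72 per arm; baseline, week 6 and week 12; correlation of week 6 with week 12 of 0.5 or 0.7; correlation of baseline with later values of 0.3; week-6 effect half the week-12 effect; 30% dropout in both arms after week 6, by chance or depending on baseline or week 6 (logistic slope 1 per SD); propensity quintiles; 10 imputations with Rubin's rules; 500 runs per scenario. Mean estimates when the truth is 11, for dropout by chance / baseline / week 6:

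| Method | Correlation 0.5 | Correlation 0.7 |
|---|---|---|
| Donors pooled, arm not in propensity model | 8.01 / 7.88 / 8.37 | 8.34 / 7.42 / 8.71 |
| Donors pooled, arm in propensity model | 8.81 / 8.05 / 8.46 | 8.91 / 7.50 / 8.80 |
| Same bootstrap within arm | 11.05 / 11.35 / 10.93 | 11.13 / 10.61 / 11.05 |
| Likelihood model, observed visits | 11.02 / 11.31 / 11.07 | 11.12 / 10.67 / 11.17 |

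Power was 50 to 69% with pooled donors, 75 to 84% within arm, and 81 to 89% for the likelihood model. Putting arm in the propensity model does not restore the effect, because it does not restrict donors to one arm.

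A separate, simpler simulation (dropout depending on one baseline covariate, 20 imputations, 1000 runs) gave 7.8 points and 57% power pooled, against 11.0 and 81% within arm.

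**4. Single imputation, no true effect.** Within-arm donors, one imputation treated as real data: rejection 10 to 20% across the assumed scenarios, and 14% in the simpler simulation (3000 runs). In that simulation, 20 imputations with Rubin's rules gave 6%.

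**5. Abstinence, 32% against 10%** (800 runs, dropout by chance / baseline). Pooled donors gave a difference of 15.4 / 16.1 points without arm in the propensity model and 18.5 / 16.4 with it, with power 53 to 67%. Within arm it was 22.1 / 22.0, with power 80 to 81%.

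**6. Below 10%.** Take 7 of 72 missing per arm: 14/144 = 9.7%. Let g be the amount by which dropouts do worse than their observed scores predict. Then

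bias = (7/72) x (g in doxazosin - g in placebo).

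With g = 10 or 20 in doxazosin and 0 in placebo (assumed), bias = 0.97 or 1.94 points in favour of the drug. SE with 65 observed per arm = 20 x sqrt(2/65) = 3.51, so null rejection is 5.9% or 8.6%. With equal g in both arms the bias is zero. With a 9 and 5 split and equal g it is (4/72) x 10 or 20 = 0.56 or 1.11.

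**The case against.** Several points on the other side stand.

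- **The plan does not decide to pool donors.** A reader might infer that it does. The text is silent on donor arm; pooling is what follows from grouping on the propensity score alone.
- **The plan does not call for a single imputation.** The approximate Bayesian bootstrap is normally a multiple-imputation step. The figures in step 4 show what the silence permits, not what is prescribed.
- **Hypothesis 1 may be unaffected.** A REML mixed model can use incomplete records. Fitted to observed visits, it shows no CAPS dilution. The plan does not say it will be used that way, and this does not help the logistic regression.
- **Pooled donors need not produce false positives.** In the equal-dropout runs with 10 imputations, null rejection with pooled donors was 0.4 to 6.0%, so the cost there is power. A spurious effect needs dropout to depend on response in opposite directions by arm, and nothing in the documents suggests that.
- **The under-10% statement is hedged and secondary.** It is offered as generally true, so reading it as an absolute guarantee overstates it. The plan expects to be above 10%, and the attrition analyses carry no threshold. The hedge does not rescue a claim that extends to every missing-data mechanism.
- **Sparse abstinence data limit the remedy.** With 72 x 0.7 = 50.4 observed placebo participants, a 5% rate gives about 2.5 abstainers and a 10% rate about 5. Ordinary logistic imputation within arm can break down on such counts.

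**Conclusion.** The concern holds in a conditional form. At the dropout the plan expects, its imputation step is the likely route, and as written it neither keeps donors within arm nor states multiple imputation, a combining rule or the analyses that use the values. If it is followed literally and its values feed the tests, the CAPS difference falls from 11 to about 7.4 to 8.9 points, with power roughly 50 to 70% against 75 to 84% within arm. The abstinence difference falls from 22 to about 15 to 19 points. A single imputation would put type I error at about 10 to 20%.

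The 0.7 multiplier follows from equal 30% dropout and arm-blind donors; the simulated ranges rest on assumed correlations and dropout models. The omissions stand without any of these figures.

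The no-bias statement below 10% is wrong as a rule, but its effect in the example is modest: 1.0 to 1.9 points and 6 to 9% null rejection, or no bias if the gap and the missing fraction are the same in both arms. The section admits that missing-not-at-random data can bias findings and plans no sensitivity analysis for it. This should be corrected before unblinding.

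**What to change.** 1. Delete the under-10% no-bias statement, the argument from randomization and the 10% trigger.
2. Hypothesis 1: take the effect from the REML mixed model already planned, fitted to all observed CAPS-5 visits without prior imputation, and say so.
3. Hypothesis 2, logistic and GEE: use multiple imputation within arm, with earlier outcomes informing the imputation, a stated number of imputations, and Rubin's rules. Because only 5 to 10% abstinence is expected on placebo, choose a method that tolerates sparse cells: penalised logistic imputation, or the plan's own bootstrap run within arm. The within-arm bootstrap recovered the 22-point difference in step 5, under dropout by chance or baseline only; penalised imputation was not simulated and should be tried on simulated data first.
4. Add missing-not-at-random sensitivity analyses: a delta or tipping-point analysis for CAPS-5, and dropouts counted as not abstinent for Hypothesis 2.

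The cost is SAP wording, some programming and a few extra tables. No new visits or participants are needed.

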- PTSD Checklist (PCL-5; Weathers et al., 2013): The PCL-5 is a 20-item self-report measure. The PCL-5 is similar in form to the PTSD Checklist (PCL) based on the DSM-IV (Weathers et al., 1993), which has excellent psychometric characteristics for screening and as a secondary indicator of PTSD symptom severity. The past month version (assessing symptoms for the past month) will be used at baseline and follow-up sessions while the past week version (symptoms from the past week) will be used for weeks 1 – 12 of treatment.
- Life Events Checklist for DSM-5 (LEC-5; Weathers et al., 2013): The LEC-5 assesses lifetime exposure to trauma. It includes the list of 16 different events from the original LEC (Gray et al., 2004). In addition, two items screen for military sexual trauma. The primary addition to the LEC-5 is a category involving occupational exposure (e.g., paramedic, police, military, or other first responder"). The psychometric properties of the LEC-5 have not yet been established, however the measure is nearly identical to the original LEC, which has been shown to demonstrate good convergence with the Traumatic Life Events Questionnaire (average kappa = 0.55) and correlate with the Posttraumatic Stress Disorder CheckList (reliability coefficients 0.34 to 0.48), and it demonstrates good test-retest reliability over 7-days.
- Childhood Trauma Questionnaire-Short Form (CTQ-SF; Bernstein et al., 2003): The CTQ is a 28-item self-administered inventory that assesses childhood abuse and neglect. The CTQ-SF is based on a 5-point Likert scale with response options ranging from *Never true* to *Very often true* and contains five subscales including physical, sexual, and emotional abuse, and physical and emotional neglect. The CTQ-SF exhibited good internal consistency with alphas ranging from .81 to .93 in a sample of substance abuse treatment seeking veterans (Bernstein et al., 2003).

Substance Use

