Power. This study is powered to estimate the effects of doxazosin on significant reduction in PTSD symptoms at the end of treatment (see Hypothesis 1), and increased abstinence rates at the end of treatment (see Hypothesis 2). Placebo rates of reduction in CAPS scores are conservatively estimated to be 20% (Zohar et al., 2002). In a small pilot study, De Jong et al. (2010) found ~31% reduction in CAPS scores using 4mg doxazosin. A sample of 100 participants will provide 80% power with a .05 type 1 error rate to detect a difference in the reduction of CAPS scores between doxazosin (31±20%) and placebo (20±20%). Placebo rates of drug abstinence are estimated from established double-blind placebo controlled trials. Continuous abstinence from weeks 9-12 is observed in 10-15% of treatment seekers without co-occurring PTSD (Shorter et al., 2013) so we anticipate an attenuated rate of 5-10% in the placebo group. Although there is limited information on the effectiveness of doxazosin in addiction, a sample of 100 subjects (50 in each arm) will provide adequate power to detect an abstinence rate as low as 32% in the doxazosin when the placebo cessation rate is 10% and as low as 23% when the placebo rate is 5%. Due to the nature of the study population, we anticipate ~30% dropout rate; thus the number of subjects randomized is inflated to 144, n=72 randomized to each treatment arm of the study.

Power calculations for the neuroimaging component are based on previous studies of individuals with PTSD or substance use disorders. Based on our previous work and the extant literature, we conservatively estimate that approximately 88/144 will be eligible and volunteer to participate in the neuroimaging component. Of these 88 participants, half (n=44) will be assigned to doxazosin and half to placebo (n=44). Hypotheses 3A and 3B will, therefore, involve the subset of 44 participants who complete the neuroimaging component and receive doxazosin treatment. A recent study of Veterans with PTSD (n=14) as compared to controls (n=15) observed significant differences in PFC-AMY resting state connectivity (Sripada et al., 2012). The effect size for this difference was 0.8 (measured using Cohen's d). Thus, power (1- β) reaches .80 with a total sample size of N=26 (two-tailed, alpha=.05). Another recent study of cocaine-dependent individuals (N=45) found that

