Hypothesis 2: Participants who receive doxazosin, as compared to placebo, will evidence significantly greater reductions in SUD severity. To test this hypothesis, logistic regression analysis will be used to examine rates of abstinence (TLFB, biological tests) during the end of treatment phase (week 9-12). Weekly point prevalence abstinence will be examined using generalized linear models under a generalized estimating equations (GEE) framework. GEE models will allow for examination of differential effects of doxazosin vs. placebo on abstinence over the course of the treatment phase of the study. Weekly abstinence (yes/no) as well as amounts (e.g., standard drink units, dollar amount of substances) will be examined over time to determine if treatment is effective in reducing substance use when abstinence is not achieved.

Hypothesis 3A: PFC-AMY connectivity at rest and in response to trauma vs. neutral cues will predict amount of change in PTSD symptoms (CAPS-5).

Hypothesis 3B: PFC-AMY connectivity at rest and in response to substance vs. neutral cues will predict time to first use of alcohol or drugs (TLFB).

The following preprocessing and analytical parameters will be used to test hypotheses 3A-3B. **Preprocessing:** Post-acquisition preprocessing and statistical analysis of all of imaging data will be performed using FEAT (fMRI Expert Analysis Tool) Version 5.98, part of FSL (FMRIB's Software Library). Data will be preprocessed using scripting tools from FEAT. Non-brain signal will be removed using FSL's BET brain extraction. Scans will be corrected for motion using FSL's linear registration and scans will be spatially smoothed using a Gaussian kernel of 8 mm FWHM. Participants with head motion ≥ 0.2 mm will be excluded from the analyses [1]. Motion artifacts will be identified and scrubbed from each subject's data. Scans will be spatially co-registered with a standardized anatomical template (Montreal Neurological Institute) using a 12 parameter affine transformation.

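### The H1 mixed model names neither the baseline PTSD score nor the two stratification factors; prespecifying them is a nearly free improvement in efficiency

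*Combined protocol and SAP*

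**What the plan says.** Under Statistical Analyses, Hypothesis 1, "generalized linear mixed effects models will be employed to assess reduction in CAPS-5 and PCL-5 total scores during the treatment phase", fitted by REML, with model-based estimates used for group tests over time. No covariate is listed.

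Under Randomization, the plan states: "The randomization will be stratified by (1) PTSD severity (PCL total score) and (2) AUD severity (AUDIT total score) for a total of four strata", by an urn scheme. The reason given is this: "The purpose of stratification is to distribute these potential prognostic factors equally across treatment groups". The same paragraph expects some gain in power if the factors are predictive.

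Under General, "Baseline clinical and demographic characteristics will be collected and contrasts performed between treatment groups". Nothing says whether those contrasts affect the outcome models.

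Under Power, "A sample of 100 participants will provide 80% power with a .05 type 1 error rate" for reductions in CAPS of 31±20% against 20±20% at the end of treatment. With about 30% dropout, 144 are randomized.

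Table 1 places CAPS-5 at baseline and weeks 6, 12 and 18, and PCL-5 at week -1, week 0 and weekly thereafter. On PCL-5, under Assessment Instruments: "The past month version (assessing symptoms for the past month) will be used at baseline and follow-up sessions while the past week version" serves weeks 1 to 12.

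Hypothesis 2 uses logistic regression for abstinence in weeks 9-12. In addition, "Weekly point prevalence abstinence will be examined using generalized linear models under a generalized estimating equations (GEE) framework". No covariate is named there either. The TLFB covers alcohol and drugs for the 60 days before the study.

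**The concern.** The plan treats PTSD severity and AUD severity as prognostic when it allocates participants, then leaves both out of the analysis model. The word reduction implies that the baseline score enters H1 somehow. It could be subtracted, used as a denominator, modelled as a repeated outcome or fitted as a covariate, and these choices differ in efficiency.

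For PCL-5 the choice also affects meaning. Subtracting a past-month score from a past-week score mixes two recall windows. With PCL-5 at both week -1 and week 0, the baseline visit is not identified.

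Two things are at stake. One is precision in a trial planned on about 100 analysed participants with little reserve. The other is that the model terms stay open until after the baseline contrasts have been seen.

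**Working it through.** **Inputs from the Power paragraph:** difference 11, SD 20, 50 per arm, alpha .05. Two-sided testing is assumed, because sidedness is not stated for H1. The percentages are treated as points on a change scale.

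**Reproducing the plan's figure.** SE = 20 × √(2/50) = 4.0. Power = Φ(11/4.0 − 1.96) = Φ(0.79) = .785, against 80% stated. Exactly 80% needs 52 per arm, or 104. Dropout: 100/0.70 = 143, against 144 stated. Both agree closely.

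**Baseline as a covariate.** Let r be the baseline-to-week-12 correlation and k the week-12 SD divided by the baseline SD. The documents give neither, so both are assumed. Relative to a change score, the variance of the adjusted contrast is

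k²(1 − r²) / (1 + k² − 2rk).

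Denominator minus numerator is (1 − rk)², which is never negative. In large samples adjustment therefore never loses to the change score, and it ties only at rk = 1. Power is Φ(11 / (4.0 × √ratio) − 1.96).

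| k | r | variance ratio | power |
|---|---|---|---|
| 1 | .3 / .5 / .7 | .65 / .75 / .85 | .927 / .888 / .847 |
| 1.25 | .3 / .5 / .7 | .784 / .893 / .981 | .874 / .829 / .793 |
| 1.5 | .3 / .5 / .7 | .871 / .964 / .998 | .838 / .800 / .786 |

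For k = 1 the number needed for 80% power falls from 104 to 68, 78 or 90.

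**Mixed-model simulation.** There were 6,000 runs per cell: 144 randomized by urn in four strata, 30% random dropout, unstructured covariance. Assumptions include median-split strata, half the effect at week 6 and no imputation. Power at r = .3/.5/.7:

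| k | arm-specific baseline means | + baseline covariate | + baseline and strata |
|---|---|---|---|
| 1 | .820 / .809 / .806 | .916 / .879 / .851 | .915 / .873 / .842 |
| 1.25 | .812 / .793 / .788 | .866 / .821 / .794 | .863 / .819 / .790 |
| 1.5 | .800 / .780 / .787 | .831 / .789 / .790 | .824 / .784 / .786 |

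The baseline gain is about 4-10 points at k = 1 and 0.3-5.5 points otherwise. Once baseline is in, strata that predict nothing further cost at most 0.9 points. If the AUDIT stratum explains a further 10%, they add 2.0-4.7 points (k = 1).

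**Leaving out strata that matter.** If balanced strata explain a share R² of the outcome variance and are omitted, the model overstates the variance of the contrast. The true size is then 2Φ(−1.96/√(1 − R²)): .039 at R² = .10 and .024 at R² = .25. Simulation gave .040 and .028, against about .05 with strata included. The unadjusted test is conservative, not anticonservative.

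**H2.** At 10% vs 32% about 5 + 16 = 21 abstainers are expected among 100; at 5% vs 23%, about 2.5 + 11.5 = 14. In simulation (8,000 runs per cell, score test), adding baseline use changed power by −1.2 to −0.2 points when it was not prognostic, −0.9 to +0.4 at an assumed log-odds of −0.3 per SD, +0.7 to +2.9 at −0.7, and +6.2 to +7.8 at −1.4. Adding the strata as well gave size of 5.0-7.6%.

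**The case against.** The strongest reply is that the plan does not exclude an efficient model. Baseline CAPS-5 as a repeated outcome with a common mean across arms fits the wording of Hypothesis 1 and already has the efficiency of covariate adjustment, so the gain would be zero. This stands: the range starts at zero, and the defect is silence about the model form.

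The larger gains also need equal SDs. Requiring current PTSD at entry could narrow the baseline spread and make k exceed 1, although the documents give no SD to settle it. The scale matters too. If percent reduction is analysed and is independent of baseline, adding baseline changed simulated power by −0.4 to −0.5 points. On total scores, which Hypothesis 1 names, 2.5-5.0 points remained under the same assumption.

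Finally, Missing Data plans propensity-score imputation when more than 10% is missing, and about 30% dropout is expected. One rough check of such an imputation (800 runs per cell, noise of 1-2 points, k = 1) gave gains of 8.5/8.1/1.8 points at r = .3/.5/.7, against 12.3/10.4/3.9 in completers. The direction held; the size is not established.

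For H2 the objection largely succeeds. With 14-21 events, one covariate is a trade-off, and AUDIT covers alcohol only while entry allows any SUD.

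**Conclusion.** The point holds for H1 as a free improvement. Relative to a change score at 78.5% power, naming the baseline score gives about 85-93% with equal SDs and 79-87% with week-12 SDs 1.25 to 1.5 times baseline, for assumed r = .3-.7 and complete data at 50 per arm. It gives nothing if a common-baseline-mean model was intended. Strata add little after baseline, cost at most about 1 point, and keep the test from being conservative if they are prognostic.

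A reader might infer that the trial is underpowered or its test invalid because of the omission. The documents do not support that. The stated power reproduces without any covariate, randomization protects the comparison from bias, and omitting balanced strata only makes the test conservative. Nor do the documents say that baseline is excluded, or that covariates will be picked from the baseline contrasts; they leave both open. For H2 they give no evidence that baseline use is prognostic enough to require adjustment.

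**What to change.** **H1.** State in the SAP that the model contains arm, visit, arm-by-visit, baseline score and the two stratification factors, and that the week-12 arm contrast is the test, matching the end-of-treatment effect used for power. For CAPS-5, baseline may be a covariate or a repeated outcome with a common mean in both arms; say which. For PCL-5, enter baseline as a covariate only, and name the visit and form version used. State that the between-arm baseline contrasts do not alter the model terms.

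**H2, optional.** If wanted, prespecify one baseline TLFB measure, such as percent of days using, in the logistic and GEE models. The odds ratio then becomes conditional, so report a marginal risk difference beside it. Keep strata-adjusted models as sensitivity analyses.

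**Cost.** A few lines of text and no new data. Power falls by up to about 1 point if the H1 strata, or the H2 covariate, turn out not to be prognostic.
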